### 6.6 *What data will be collected during the study and how that data will be obtained.*

Data from self-report measures will be collected online using Qualtrics which is a safe and secure survey website platform previously used by Florida State University. Data will be coded and stored on a password-protected file.

## 7.0 Data and Specimen Banking\*

## PROTOCOL TITLE: Development and Evaluation of a Tonic Immobility Focused Psychoeducational Intervention - RCT

7.1 *If data or specimens will be banked for future use, describe where the specimens will be stored, how long they will be stored, how the specimens will be accessed, and who will have access to the specimens.*

All data that will be used for analysis. Safeguards include: (a) ensuring that all project staff and participants are well informed about regulations pertaining to confidentiality, (b) the use of study ID numbers as opposed to names on all data forms, (c) requiring that all subject files be password protected if online, and (d) any paper copies will be stored in locked file cabinets. All study personnel will have access to stored data.

7.2 *List the data to be stored or associated with each specimen.*

Data will include de-identified study ID numbers, self-report data, and qualitative written responses to open ended questions.

7.3 *Describe the procedures to release data or specimens, including: the process to request a release, approvals required for release, who can obtain data or specimens, and the data to be provided with specimens.*

N/A

## 8.0 Sharing of Results with Subjects\*

8.1 *Describe whether results (study results or individual subject results, such as results of investigational diagnostic tests, genetic tests, or incidental findings) will be shared with subjects or others (e.g., the subject's primary care physicians) and if so, describe how the results will be shared.*

N/A

## 9.0 Study Timelines\*

9.1 Participation is expected to last 1 month. We anticipate that it will take about **18 months** to enroll all participants

## 10.0 Inclusion and Exclusion Criteria\*

10.1 Student participants who endorse prior TI experience during the subject pool screening process will be invited to complete a Qualtrics survey to determine eligibility. Interested participants will be asked to sign-up for the current study using the Sona-systems website. Community participants will be directed to the Qualtrics survey through flyers and online advertisements. Eligible community participants will be contacted via phone to schedule their initial appointment.

10.2 Eligible participants must be 18 years or older and have endorsed prior TI experience. Study participants will be selected for the

## PROTOCOL TITLE: Development and Evaluation of a Tonic Immobility Focused Psychoeducational Intervention - RCT

current investigation based on prior TI experience (TIQ items A & B) and elevated posttraumatic stress symptoms (PCL-5). Exclusion criteria includes individuals who have not endorsed past TI behavior and are not 18 years or older.

*10.3 Indicate specifically whether you will include or exclude each of the following special populations: (You may not include members of the above populations as subjects in your research unless you indicate this in your inclusion criteria.)*

- *Adults unable to consent:* Excluded
- *Individuals who are not yet adult:* Excluded
- *Pregnant women:* Excluded
- *Prisoners:* Excluded

## 11.0 Vulnerable Populations\*

*11.1 If the research involves individuals who are vulnerable to coercion or undue influence, describe additional safeguards included to protect their rights and welfare.*

The current study will not involve pregnant women, prisoners, individuals under 18 years old, or cognitively impaired.

## 12.0 Local Number of Subjects

*12.1 Indicate the total number of subjects to be accrued locally.*

120 participants will be enrolled from Florida State University and the Tallahassee, FL area.

## 13.0 Recruitment Methods

*13.1 Describe when, where, and how potential subjects will be recruited. If recruitment will involve a non-FSU site, describe whether site approval for recruitment is required, and attach documentation of site approval.*

Participants will be recruited from the FSU undergraduate subject pool and the Tallahassee community. Student participants will be recruited from the psychology undergraduate research pool. Community participants will be recruited via online advertisements.

*13.2 Describe the source of subjects.*

All participants will be recruited from Florida State University and Tallahassee, FL.

*13.3 Describe the methods that will be used to identify potential subjects.*

Individuals will be identified as potential participants if they are 18 years or older and have endorsed past TI experience. Potential student participants who endorse prior TI experience during the subject pool screening process will be invited to complete a

PROTOCOL TITLE: Development and Evaluation of a Tonic Immobility Focused Psychoeducational Intervention - RCT

Qualtrics survey to determine eligibility. Community participants will be directed to the Qualtrics survey to determine eligibility.

Eligible participants will then be contacted via phone to schedule their initial appointment.

*13.4 Describe materials that will be used to recruit subjects. (Attach copies of these documents with the application. For advertisements, attach the final copy of printed advertisements. When advertisements are taped for broadcast, attach the final audio/video tape. You may submit the wording of the advertisement prior to taping to preclude re-taping because of inappropriate wording, provided the IRB reviews the final audio/video tape.)*

Recruitment methods include flyers posted in the community and online advertisements via social media platforms (e.g. Facebook, twitter).

*13.5 Describe as applicable whether and how subjects will be paid, earn course or other credits, reimbursed or provided with any financial or other incentive, token or gift for taking part in the research. Include a description and schedule of the total amount or value as well as the timing of any payments, credits, reimbursement or other incentive, token or gift. Indicate how if at all any amount is pro-rated for research visit or activity completion, and whether and how subjects' refusal to answer any question or subjects' withdrawal from or discontinuing taking part in the study or any study activity will reduce or preclude subjects from earning part or all of such any payment, credit, reimbursement or other incentive, token or gift.*

*Also describe the proposed method (how, by whom, form etc.) of payment/disbursement. While payment should not be contingent upon completion of the entire study, a proportion or progressive partial payment as an incentive for completion of the study is acceptable.*

Student participants will receive 1.5 course credits for completion of the baseline appointment and 0.5 credits for each follow-up appointment. Thus, participants will receive 2.5 credits in total for completing all study appointments. Participants who refuse to answer any question or withdraw from the study will still receive compensation for their appointment.

Community participants will receive a \$30 gift card for completion of the baseline appointment and a \$10 gift card for each follow-up appointment. Thus, participants will receive \$50 in total for completing all study appointments. Participants who refuse to answer any question or withdraw from the study will still receive compensation for their appointment.

PROTOCOL TITLE: Development and Evaluation of a Tonic Immobility Focused Psychoeducational Intervention - RCT

## **14.0 Withdrawal of Subjects\***

*14.1 Describe anticipated circumstances under which subjects will be withdrawn from the research without their consent.*

Possible reasons for removal include failure to complete the TIP intervention or self-report measures.

*14.2 Describe procedures that will be followed when subjects withdraw from the research, including partial withdrawal from procedures with continued data collection.*

The participant will be told they can leave the research at any time and it will not be held against them. All data collected prior to withdrawal will be securely stored and analyzed unless otherwise requested. Participants will be able to contact the PI to request the removal of their data, if so desired.

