**6.0 Procedures Involved\***

- 6.1 The study adheres to a randomized controlled trial (RCT) design. Participants will be randomized to either the TIP or HET condition. Randomization will be stratified based on undergraduate vs. community member status. For each group, a random number table will be generated in Excel with either 1 = TIP or 2 = HET assigned to each participant ID. After completion of consent, the participant will receive their ID (assigned in sequential order) and the research assistant will prepare the corresponding treatment.

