## PROTOCOL TITLE: Development and Evaluation of a Tonic Immobility Focused Psychoeducational Intervention - RCT

6.2 The study proposes to enroll 120 participants to test the efficacy of the TIP intervention, compared to a HET control condition. All data collection will be conducted using Qualtrics. The study will be comprised of a total of three time points: Baseline, Week 1 follow-up, and Month 1 follow-up.

First, eligible participants will read and sign an informed consent that outlines all study procedures, details limits to confidentiality, and emphasizes that participants may discontinue participation at any time with no penalty.

The first appointment, baseline, will include pre-intervention self-report measures, the completion of one of the two interventions (TIP or PHET), and post-intervention self-report measures. The baseline appointment is expected to take 90 minutes. Participants will be compensated with a \$30 gift card or 1.5 course credits. All baseline procedures will be conducted either in-person within the Anxiety and Behavioral Health Clinic research suite or virtually via HIPAA-compliant Zoom. For in-person sessions, all COVID-19 related federal, state, and local guidelines as well as FSU IRB regulations will be followed. See section 6.3 for further information on COVID-19 safeguards.

The second and third appointments, week 1 and month 1 follow-up, will be completed online. Participants will be contacted via email and asked to complete a battery of self-report measures via a Qualtrics survey link. The questionnaire is expected to last 30 minutes and participants will be compensated either a \$10 gift card or 0.5 course credits for the completion of each appointment.

After the completion of the month 1 follow-up appointment, participants will be debriefed and individuals in the control condition will be given the opportunity to receive the active treatment condition.

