### Interventions

HET has been used in prior research studies with no adverse effects. Content is related to healthy living and stress management, and not expected to cause distress.

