## PROTOCOL TITLE: Development and Evaluation of a Tonic Immobility Focused Psychoeducational Intervention - RCT

TIP has been modeled after a previous intervention which has been used in several studies and has a high level of acceptability as well as gold-standard evidence-based treatments for trauma. Although the information presented in the training should be no more anxiety-provoking than situations experienced in day-to-day life, it is possible that some participants may have strong emotional or physical reactions to information covered in the intervention. However, we believe prolonged distress is unlikely and feel that most participants will derive benefit from the interventions.

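### Section 14.1 lets the team remove randomised participants for not completing TIP or the questionnaires, so week 1 and month 1 outcomes can be lost for a post-randomisation reason that may differ by arm.

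*Combined protocol and SAP*

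**What the plan says.** All references are to the combined protocol and SAP.

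- **14.1**, on withdrawal by the study team without the participant's consent: "Possible reasons for removal include failure to complete the TIP intervention or self-report measures". The list is open and discretionary. It sets no threshold, names no decision-maker, and does not mention HET.
- **14.2**: "All data collected prior to withdrawal will be securely stored and analyzed unless otherwise requested". The form's prompt asks about partial withdrawal with continued data collection; the answer does not address it.
- **6.1**, on timing: "After completion of consent, the participant will receive their ID (assigned in sequential order) and the research assistant will prepare the corresponding treatment".
- **6.2**: the baseline appointment includes "the completion of one of the two interventions (TIP or PHET), and post-intervention self-report measures". For week 1 and month 1: "Participants will be contacted via email and asked to complete a battery of self-report measures via a Qualtrics survey link".
- **4.1**: data collection runs until every enrolled participant has completed Month 1. It does not say whether a removed person still counts.
- **15.1**, on HET: "Content is related to healthy living and stress management, and not expected to cause distress". On TIP: "it is possible that some participants may have strong emotional or physical reactions to information covered in the intervention", although its content "should be no more anxiety-provoking than situations experienced in day-to-day life". The same section lets participants skip sensitive parts of the measures.
- **17.1**: SPSS regressions are planned for posttreatment guilt, posttreatment shame and week 1 PTSD symptoms, with no covariates and no missing-data method stated. Latent difference score models are planned across all timepoints, with FIML where possible. No analysis set is defined.

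**The concern.** Both reasons in 14.1 can arise only after the arm is assigned. Removing people on such grounds takes away the protection of randomisation for every outcome not yet collected. The intervention ground names only one arm, and the protocol itself foresees strong reactions to TIP but no distress from HET. Those who stop may therefore differ between arms in guilt, shame or PTSD symptoms, which are the outcomes under test. If those removed from TIP would have scored worse, the comparison tilts toward TIP; if better, against it.

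The questionnaire ground adds an ambiguity. Section 15.1 allows skipping, and 14.1 does not say whether a skipped section counts as failure to complete.

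**Working it through.** The plan gives no alpha, power, effect size or non-completion rate, so there is no figure to reproduce. The point rests on the text.

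**What removal itself costs**

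1. Consent, then the ID that fixes the arm, then the intervention (6.1, 6.2). Anyone who fails to complete TIP is already randomised.
2. A person who leaves the baseline appointment early has no posttreatment guilt or shame score whether or not they are formally removed. That loss comes from leaving, not from 14.1.
3. What removal adds is the loss of week 1 and month 1 scores. Under 6.2 these need only an emailed link.
4. The questionnaire ground applies to both arms and would catch many HET participants who leave early. The asymmetry is therefore partial, and the omission of HET may be a drafting slip.

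**Illustration of scale**

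Assumptions, none from the documents except N = 120: 60 per arm; two-sided alpha 0.05; outcome SD 1; a share p of an arm removed and missing from the comparison; those removed D worse than those kept.

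The mean of those kept exceeds the full-arm mean by p × D, so bias = p(TIP) × D(TIP) − p(HET) × D(HET). Error rates use the normal approximation.

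| Removal, TIP vs HET | D | Bias (SD) | Type I error |
|---|---|---|---|
| 5% vs 0 (3 people) | 0.5 | 0.05 × 0.5 = 0.025 | 5.2% |
| 5% vs 0 | 1.0 | 0.05 | 5.8% |
| 10% vs 0 (6 people) | 0.5 | 0.05 | 5.8% |
| 10% vs 0 | 1.0 | 0.10 | 8.3% |
| 10% vs 5% | 0.5 | 0.05 − 0.025 = 0.025 | 5.2% |
| 10% vs 5% | 1.0 | 0.10 − 0.05 = 0.05 | 5.8% |
| Equal rates, equal D | any | 0 | 5% |

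D = −0.5 gives the same size of bias against TIP.

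With adjustment for baseline, at an assumed baseline–outcome correlation r = 0.6, simulated bias is below 0.003 SD if removal depends only on baseline. If removal depends on the outcome, bias is p × D × (1 − r²), with 1 − 0.36 = 0.64. That gives 0.016–0.032 SD at 5% (simulated error 4.8–5.9%) and 0.032–0.064 SD at 10% (5.5–7.4%).

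For scale, the difference detectable with 80% power is (1.960 + 0.842) × √(2/60) = 0.51 SD.

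These rows can be charged to 14.1 only for week 1 and month 1 outcomes (step 3).

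**What later scores recover for a missing posttreatment score**

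Assume that baseline correlates 0.6 with every later score, that post-intervention correlates 0.5, 0.6, 0.7 or 0.8 with week 1 and 0.1 less with month 1, and that week 1 and month 1 correlate as post-intervention and week 1 do. The factor 0.64 then falls to 0.609, 0.545, 0.452 or 0.333, a cut of 5%, 15%, 29% or 48%. Later scores help, but collecting the post-intervention score itself helps more.

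**The case against.** The strongest reply is that this is permissive template wording in a trial with one intervention session, and that the plan already limits the damage. Data gathered before withdrawal are analysed. FIML is planned for the latent difference score models, whose first change in guilt and in shame is the same early contrast as the posttreatment regressions. Section 4.1 continues data collection until all enrolled participants finish Month 1, and 6.2 does not make the follow-up email depend on finishing the intervention. Participants are paid even if they withdraw (13.5), and the protocol expects little distress, so non-completion may be rare.

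Most of this stands, and it rules out a stronger reading. A reader might infer that removed participants are dropped from the analysis, or that a completers-only comparison is planned. The documents say neither. Section 17.1 speaks of random assignment and then compares by condition, so analysis as assigned may well be intended.

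Four things remain. Section 14.2 is worded for people who withdraw, and whether it covers people removed is not stated. Earlier data do not replace week 1 and month 1 scores never collected. FIML is conditional and is not stated for the SPSS regressions. Section 4.1 does not settle the status of a removed participant.

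On skipped items, the payment rule in 13.5 and the permission in 15.1 suggest that skipping is not meant as failure to complete. A short clarification is enough.

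**Conclusion.** The concern holds as a flaw in the written removal rule. Section 14.1 permits removal after randomisation on grounds that name one intervention and not the other, and nothing provides for follow-up of those removed. If the rule is used, the risk is a bias of unknown size and direction in week 1 and month 1 outcomes, negligible if removals are few or similar in both arms.

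The figures rest wholly on assumed rates, differences and correlations. They do not show that this trial's error rate is inflated or that the result would favour TIP, and they should not set the severity. The change is worth making because the rule is explicit and the remedy is cheap. Confidence is medium, since how often the rule would be used is unknown.

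**What to change.** 1. **14.1.** Say that not completing either intervention, or a questionnaire, is not a reason for removal from data collection, and reconcile this with the permission to skip in 15.1. Participants remain free to stop or withdraw.
2. **6.2 and 14.2.** Offer the post-intervention measures, without requiring them, to anyone in either arm who stops early. Send the week 1 and month 1 links to everyone randomised who has not withdrawn consent.
3. **17.1.** State that all randomised participants are analysed by assigned condition and that the early-outcome regressions adjust for the baseline score. For missing posttreatment scores, use a likelihood or imputation method that includes the later guilt and shame scores, as the planned latent difference score models with FIML already can.
4. **Reporting.** Give intervention completion by arm. Any completer analysis should be supportive and defined the same way in both arms.

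**Cost.** Apart from wording, follow-up costs at most 2 × $10 = $20, or 2 × 0.5 = 1.0 credit, per retained person. For 6 people (5% of 120) that is $120; for 12 (10%), $240. The post-intervention measures need no extra payment, because 13.5 already pays for the appointment.

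**Downside.** If non-completers gain nothing, keeping them dilutes the effect. At 5% non-completion in TIP, 0.511 × 0.95 = 0.486 SD and power falls from 80% to 76%; at 10%, 0.511 × 0.90 = 0.460 SD and 71%. Analysing completers only would give 79% and 78%, but would give up the comparison as randomised.

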## **15.0 Risks to Subjects\***

*15.1 List the reasonably foreseeable risks, discomforts, hazards, or inconveniences to the subjects related to the subjects' participation in the research. Include as may be useful for the IRB's consideration, a description of the probability, magnitude, duration, and reversibility of the risks. Consider physical, psychological, social, legal, and economic risks. For each of these risks, describe in detail how the risks will be minimized.*

The risks to human subjects in the proposed study are minimal. Nevertheless, precautions will be taken to minimize participants' risk in the proposed study. All individuals will be informed of the nature of the investigation and the types of assessments and procedures. Participants will be asked to sign an informed consent statement prior to participating in the project. The specific potential risks involved in the proposed investigation are enumerated below:

### Self-report measures

It is unlikely that participants will be at risk for emotional or physical harm as a result of study participation. However, there is a slight possibility that participants may experience emotional discomfort or distress while completing study tasks. Based upon our past research, any distress reactions due to completion of questionnaires is typically acute (i.e., few minutes in duration) and relatively minor.

### Interventions

HET has been used in prior research studies with no adverse effects. Content is related to healthy living and stress management, and not expected to cause distress.

## PROTOCOL TITLE: Development and Evaluation of a Tonic Immobility Focused Psychoeducational Intervention - RCT

TIP has been modeled after a previous intervention which has been used in several studies and has a high level of acceptability as well as gold-standard evidence-based treatments for trauma. Although the information presented in the training should be no more anxiety-provoking than situations experienced in day-to-day life, it is possible that some participants may have strong emotional or physical reactions to information covered in the intervention. However, we believe prolonged distress is unlikely and feel that most participants will derive benefit from the interventions.

### Protections against risk

Confidentiality will be described during the consent process. The process will reiterate the limits of confidentiality. Data entry personnel will download the data into a dedicated, password-protected computer database as an additional on-site back-up. Computer files will be maintained on the servers and backed up daily. Computers and databases will be password protected with independent passwords known only to the PI and data entry personnel. All data will be accessible only to trained study staff. Participants' data will be de-identified and coded with ID numbers. A link between participant names and ID numbers will be kept separately in a password protected computer file. All project staff are trained and certified in HIPAA regulations, responsible conduct of research and the protection of human research subjects via Collaborative Institutional Training Initiative (CITI) courses.

The risk of emotional discomfort will be minimized by informing participants that they are allowed to skip any sensitive areas on the assessment measure and may discontinue participation at any time. All research staff will be trained to deal with sensitive clinical issues and will be available should participants need assistance.

Further, a trained graduate-level therapist, supervised by Licensed Clinical Psychologist [name], will be available to assist participants experiencing emotional discomfort, including strong emotional or physical reactions to intervention materials, at all times. Standard procedures include implementation of coping skills (e.g., deep breathing, self-soothing) to reduce distress and referral to treatment, if desired. [name] or an alternate clinical supervisor within the FSU Psychology Clinic will be on call and available during study sessions if consultation is needed.

15.2 – 15.4

N/A

